---	--	--	-------

CLINIMARK Test Plan

Clinical Evaluation of Zynex Monitoring System, Model CM-1600 PR2022-516

No anticipated risks or adverse device effects need to be assessed. No contraindications exist for use in the proposed study / study population. Any other risks to the participant associated with the device or procedure are unforeseeable at this time.

ECG / Gel Electrodes

Materials (such as the adhesive and/or gel contact) used in the electrodes may cause some skin irritations in some participants. Typical skin irritations present with redness of skin and in some cases of sensitivity as an allergic reaction. Biocompatibility testing for surface contact electrodes is a requirement of the International Organization of Standardization (ISO) 10993-9:2008 Biological Evaluation of Medical Devices. The risk in the use of ECG and other gel electrodes is believed to be minimal.

Pulse Oximetry Sensor

Pulse oximetry sensor placement involves positioning pulse oximetry sensors on the volunteer participant in the same manner that is used on hospitalized patients. The sensors may be warm to the touch. Under normal operating conditions, without electrical abnormalities or fault conditions, the sensors are not expected to overheat. If the sensors are too warm, they will be removed immediately. Clip on and soft reusable sensors exert a minimal amount of pressure. They should not cause discomfort. Adhesive sensors or tape may cause some irritations to the skin in some participants. Every effort will be made to minimize products with natural rubber or latex, and products containing natural rubber or latex will be identified. The risk involved in the use of pulse oximetry sensors is believed to be minimal.

Finger Prick Lancet

A finger prick blood analysis involves using a lancet to draw a small amount of blood from the tip of a finger. Possible risks from the finger prick procedure include: discomfort, bruising, clotting, and infection.

Peripheral Intravenous Cannula

[figure not shown]
A peripheral IV cannula will be inserted by a qualified healthcare professional. The possible risks from the IV insertion include: pain, hematoma, clotting, infection, scar formation, and infiltration.

Benefits

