The participant or legal guardian of the participant will review and sign the informed consent following a discussion of the test procedure; after all questions regarding the study have been answered; and prior to the start of any study procedures. The participant will complete the health assessment questionnaire and disclose any pertinent issues that may affect his/her health during the test. The participant or legal guardians of the participant may withdraw the participant from the study at any time. The participant may be withdrawn per the Procedure section below.

A clinician will be present to monitor the participant at all times. Safety monitoring includes ECG, SpO₂, pulse rate, respiration rate, direct observation and communication with the participant.

Adverse Event Definitions

The definitions for adverse event, adverse device effect, serious adverse event, serious adverse device effect, unanticipated adverse device effect, and their classifications are provided below (ISO 14155, 21 CFR 812.3).

- **Adverse Device Effect (ADE):** Adverse event related to the use of an investigational medical device and resulting from insufficiencies or inadequacies in the instructions for use, the deployment, installation, the operation, any malfunction of the investigational medical device, or from usage error.

Clinimark [name]	TITLE: Clinical Evaluation of the Zynex Monitoring System, Model CM-1600 ID# PR 2022-516 Principal Investigator: [name] Site ID # 001	DOCUMENT NUMBER PR# 2022-516 SHEET 24 of 30	REV 1
---	--	--	-------

CLINIMARK Test Plan

Clinical Evaluation of Zynex Monitoring System, Model CM-1600 PR2022-516

- **Adverse Event (AE):** Any untoward medical occurrence, unintended disease or injury, or any untoward clinical signs (including an abnormal laboratory finding) in participants, users, or other persons, whether or not related to the investigational medical device or investigational procedure.
- **Anticipated Serious Adverse Device Effects (ASADE):** ASADE is an effect which, by its nature, incidence, severity, or outcome has been identified in the risk analysis report.
- **Mild:** A mild adverse event is one in which the participant is aware of the event, but it is easily tolerated without intervention.
- **Moderate:** A moderate adverse event is one that causes sufficient discomfort to interfere with usual activities.

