- **Serious Adverse Device Effect (SADE):** An adverse device effect results in any of the consequences characteristic of a serious adverse event.
- **Serious Adverse Event (SAE):** A serious adverse event results in death, inpatient hospitalization, severe or permanent disability, a life-threatening illness or injury, fetal distress, fetal death, a congenital abnormality, a birth defect, or requires medical or surgical intervention to prevent permanent impairment to body or structure.
- **Severe:** A severe adverse event results in the inability to perform usual activities.
- **Unanticipated Adverse Device Effect (UADE):** A serious adverse device effect is one which, by its nature, incidence, severity, or outcome has not been identified in the current version of the risk analysis report.

Management of Adverse Event Reporting

Should the participant experience an adverse or non-typical event, the investigational staff will assess the situation and determine appropriate actions. The Medical Director and Principal Investigator will be contacted as appropriate. Adverse Events are reported through standard Clinimark procedures, IRB requirements, and per Zynex SOPs.

Records of adverse events will be recorded in the Case Report Form.

The following information will be obtained:

- Type of effect (ADE, AE, ASADE, SADE, SAE, UADE)
- Date of onset and resolution
- Intensity (mild, moderate, severe)
- Serious (yes/no)
- Relationship to device (unknown, not related, possibly related, probably related, definitely related)
- Anticipated (yes/no)
- Treatment given and / or action taken (procedure stopped, withdrawn from study, no action)

Clinimark [name]	TITLE: Clinical Evaluation of the Zynex Monitoring System, Model CM-1600 ID# PR 2022-516 Principal Investigator: [name] Site ID # 001	DOCUMENT NUMBER PR# 2022-516 SHEET 25 of 30	REV 1
---	--	--	-------

CLINIMARK Test Plan
Clinical Evaluation of Zynex Monitoring System, Model CM-1600
PR2022-516

Reporting of Serious Adverse Events and / or UADE

All SAE's, SADE, ASADE, and UADE will be reported in writing to the Principal Investigator, Medical Director, Sponsor, and IRB as soon as possible and no later than 10 working days after the Investigator first learns of the event.

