If the event results in death of a participant, the event shall be reported to the Principal Investigator, Clinimark Medical Director, Sponsor, and IRB within 24 hours of knowledge of the event.

[REDACTED]

Sponsor Records and Reports

Records 21 CFR 812.140 (b) 4,5

The following records shall be consolidated in one location and available for FDA inspection and copying:

- The name and intended use of the device and the objectives of the investigation
- A brief explanation of why the device is not a significant risk device
- The name and address of each Investigator
- The name and address of each IRB that has reviewed the investigation
- A statement of the extent to which the good manufacturing practice regulation in part 820 will be followed in manufacturing the device
- Any other information required by FDA
- Records concerning adverse device effects (whether anticipated or unanticipated) and complaints

Reporting 21 CFR 812.150 (b) 1,2,3,5,6,7,8,9,10:

The Sponsor shall prepare and submit the following complete, accurate, and timely reports:

Unanticipated Adverse Device Effect

The Sponsor shall immediately conduct an evaluation of an unanticipated adverse device effect. The results of such evaluation shall be reported to the FDA, IRB, and participating Investigators as soon as possible and not later than 10 working days after the Investigator first learns of the effect.

Withdrawal of IRB approval

Clinimark [name]	TITLE: Clinical Evaluation of the Zynex Monitoring System, Model CM-1600 ID# PR 2022-516 Principal Investigator: [name] Site ID # 001	DOCUMENT NUMBER PR# 2022-516 SHEET 26 of 30	REV 1
---	--	--	-------

CLINIMARK Test Plan
Clinical Evaluation of Zynex Monitoring System, Model CM-1600
PR2022-516

Withdrawal of IRB approval shall be reported to the FDA, IRB, and the Investigator within 5 working days after receipt of withdrawal of approval by the Sponsor.

Withdrawal of FDA approval

Withdrawal of FDA approval of an investigation shall be reported by the Sponsor to the IRB and the Investigator within 5 working days after receipt of notice of withdrawal of approval.

Progress Reports

The Sponsor shall submit progress reports to the IRB at least yearly.

Recall and device

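### On its natural reading, the ADE definition leaves out device-related reactions that arise without a fault or use error, and SADE and UADE inherit the gap (minor)

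*Combined protocol and SAP*

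**What the plan says.** Under Adverse Event Definitions, an ADE is an "Adverse event related to the use of an investigational medical device and resulting from insufficiencies or inadequacies in the instructions for use". The list of causes then continues with "the deployment, installation, the operation, any malfunction of the investigational medical device, or from usage error".

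Two further definitions build on this one:
- SADE: "An adverse device effect results in any of the consequences characteristic of a serious adverse event".
- UADE: "A serious adverse device effect is one which, by its nature, incidence, severity, or outcome has not been identified" in the current risk analysis report.

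The general AE definition is broad. It covers untoward occurrences "whether or not related to the investigational medical device or investigational procedure".

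The section on ECG / Gel Electrodes foresees a contact effect: "Materials (such as the adhesive and/or gel contact) used in the electrodes may cause some skin irritations in some participants". It mentions redness and allergic reaction and does not link them to a fault or misuse. The description of the investigational device lists electrodes as part of the CM-1600 configuration.

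Management of Adverse Event Reporting collects the type of effect, seriousness, a five-level relationship to the device and whether the event was anticipated, each as a separate item. Under Sponsor Records and Reports, the Sponsor keeps records of adverse device effects, and for one class only, "The Sponsor shall immediately conduct an evaluation of an unanticipated adverse device effect".

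**The concern.** A definition of device effects should capture what the device does to people, including when it works and is used as instructed. That is also the normal case here: equipment is checked before it is placed on the participant, and the CM-1600 is set up according to its instructions. The definition adds a cause test that a fault-free reaction fails.

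Two things are at stake. First, the type-of-effect field and the relatedness field can disagree by rule, because an event with the highest relatedness rating may have to be typed as a plain AE. Staff who follow the definition and staff who follow common sense would then code the same event differently, and the adverse device effect records could omit the electrode reactions that the protocol itself foresees. Second, a serious, unforeseen, device-related reaction without a fault would not meet the UADE definition, and only a UADE triggers the immediate Sponsor evaluation. The study is early in the device's clinical development, when unforeseen device effects matter most.

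**Working it through.** No arithmetic applies. The check is to read the definitions in order and run typical cases through them.

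1. ADE = (related to device use) AND (results from a listed cause). The listed causes are shortcomings in the instructions, deployment, installation or operation; malfunction; or usage error. They are joined by 'and resulting from', not introduced by 'including', so they restrict the class.
2. SADE = ADE with serious consequences, so whatever is not an ADE is not a SADE.
3. UADE = SADE not identified in the risk analysis report, so whatever is not a SADE is not a UADE.
4. No other available section widens the ADE definition.

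Cases, on the natural reading:

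| Case | Related to CM-1600 use | Listed cause | As written | With the fix |
|---|---|---|---|---|
| Irritation under a sound, correctly applied CM-1600 electrode | yes | no | AE only | ADE |
| Irritation traced to inadequate instructions | yes | yes | ADE | ADE |
| Irritation from a wrongly applied electrode | yes | yes | ADE | ADE |
| Irritation under a separate reference ECG lead | no | not applicable | AE only | AE only |
| Serious, related, fault-free, not in the risk analysis report | yes | no | SAE, not UADE | UADE |
| Serious, related, fault-free, in the risk analysis report | yes | no | SAE, not SADE (possibly ASADE) | SADE, not UADE |

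The first and the last two rows change. The last has the 'possibly ASADE' entry because ASADE is defined simply as an effect identified in the risk analysis report and is not expressly tied to the ADE conditions.

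Reporting routes for the serious, unforeseen, fault-free case:
- As an SAE: a written report to the Principal Investigator, Medical Director, Sponsor and IRB within 10 working days (24 hours if the participant dies).
- As a UADE: the same report, plus an immediate Sponsor evaluation with results to FDA, IRB and Investigators, not later than 10 working days after the Investigator first learns of the effect.

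The difference is the Sponsor evaluation and the report of its results, which includes FDA as a recipient.

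**The case against.** The strongest reply is that the list of causes is grammatically loose. A malfunction cannot sensibly be an object of 'inadequacies in', so at least some items must attach directly to 'resulting from', and it is unclear where the break falls. If deployment and operation are read as causes in their own right, a reaction to an electrode in ordinary operation could qualify as an ADE. This stands. A reader might infer that fault-free reactions can never be ADEs, and the text does not support anything so absolute. It supports the natural reading, with a second reading available. A safety definition that admits two readings still needs repair.

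A reader might also infer that these events go unreported. They do not. Seriousness, relatedness and expectedness are recorded for each adverse event whatever its type, and SAEs follow the same 10-working-day limit.

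Nor can one conclude that a safety table will show zero ADEs. The Statistical Analysis Plan promises a tabular summary of adverse events and specifies no ADE line. The documents give no rate of contact reactions and call the electrode risk minimal.

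The UADE consequence is also narrow. An electrode reaction of foreseen nature and severity is not a UADE under either wording if the risk analysis report lists it, and that report is not available. The definitions cite a standard and a regulation that are also not available, so agreement with them was not assessed. Site procedures or Sponsor SOPs may guide classification, but the protocol would still state a rule that they would have to override.

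**Conclusion.** Wrong as written, minor. On the natural reading, a device-related reaction without a fault, inadequacy or use error falls outside ADE, and therefore outside SADE and UADE. What can be lost is entry in the adverse device effect records and, for a serious unanticipated event only, the Sponsor evaluation with its report to FDA, IRB and Investigators. The recording of events, their relatedness ratings and the SAE reporting limit are unaffected, as is the study's objective.

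The conclusion rests on reading 'and resulting from' as a second condition, and on there being no wider definition in a document outside the protocol. The size cannot be expressed as a count or probability without an assumed reaction rate, and the finding does not need one.

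**What to change.** In the ADE definition, replace 'and resulting from' with 'including any event resulting from'. Relation to device use alone then makes an event an ADE, and the listed causes become examples. SADE and UADE follow without further change.

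The cost is one phrase, processed through the protocol's amendment route (Sponsor approval, then IRB approval), and a check that the adverse event form carries the same wording. No new data, procedures or participants are needed, because relatedness to the device is already collected for each event.

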33. Once data collection on the CM-1600 is stopped, the USB data storage can be removed. USB data storage device is to be labeled in accordance with the assigned participant identification number and the continuity of the acquired data is to be verified and/or backed-up. The CM-1600 device and accessories will be wiped down again with a disinfecting wipe. Electrodes will be disposed.
34. Blood disposal will be carried out at the Investigator site and will follow all applicable rules and regulations, including any site-specific procedures.
35. Clinimark will follow up with the participant in 24-48 hours to screen for any adverse events or complications.

Clinimark [name]	TITLE: Clinical Evaluation of the Zynex Monitoring System, Model CM-1600 ID# PR 2022-516 Principal Investigator: [name] Site ID # 001	DOCUMENT NUMBER PR# 2022-516 SHEET 17 of 30	REV 1
---	--	--	-------

CLINIMARK Test Plan
Clinical Evaluation of Zynex Monitoring System, Model CM-1600
PR2022-516

Statistical Analysis

This is a prospective, single-arm, hypothesis-generating study early in the clinical development of the Zynex CM-1600; hence, no statistical tests are required and no assumptions are made. Any statistical and data analysis will be performed by the Sponsor.

Sample Size Justification

The objective of this study is to determine if manually controlled and quantified blood loss and saline re-infusion can be identified by the non-invasive Zynex CM-1600. No statistical hypotheses have been generated for this study; therefore, the sample size of 20 participants is empirically determined to be sufficient for an early-phase hypothesis-generating study and is based on clinical judgment rather than statistical considerations.

Analysis Populations

This is a hypothesis-generating study of 20 participants; therefore, all data collected will be used and presented in the study summaries.

Statistical Analysis Plan

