The Investigator shall report to the Sponsor, within 5 working days, a withdrawal of approval by the reviewing IRB of the Investigator's part of an investigation.

Informed consent

If an Investigator uses a device without obtaining informed consent, the Investigator shall report such use to the Sponsor and the reviewing IRB within 5 working days after the use occurs.

Other

The Investigator shall, upon request by a reviewing IRB or FDA, provide accurate, complete, and current information about any aspect of the investigation.

Withdrawal, Early Termination, or Suspension of the Investigation

Participation in the study is voluntary. The participant may choose to withdraw from the study at any point. If a participant officially withdraws from the study, the laboratory staff will document the reason for withdrawal in the case report.

Participation in the study may also be stopped at any time by the Principal Investigator or by the Sub-Investigators or Sponsor for the following reasons:

- The participant's failure to cooperate fully (as determined by the Investigator in his or her sole discretion) with the required conduct of this study
- The participant's development of an illness as determined by the Investigator in his or her sole discretion
- A determination by a Clinimark representative (in his or her sole discretion), for whatever cause, that the study should be discontinued
- A determination by the Sponsor (in his or her sole discretion), for whatever cause, that the study should be discontinued

The collection of data for study participants will cease in the following cases:

- Participant completes all study requirements
- Participant withdraws consent
- Investigator's decision that it is in participant's best interest to be discontinued from the study
- Participant death
- Adverse event other than death requiring withdrawal of the participant from the study
- Determination that the participant was ineligible for the study

No follow-up procedures for withdrawn or discontinued participants are required, unless such is required at the Investigator's discretion.

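### The withdrawal section makes follow-up optional for withdrawn participants, while Procedure step 35 sets a 24-48 h safety contact without exception, and no visible text says which governs

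*Combined protocol and SAP*

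**What the plan says.** Four parts of the combined protocol and SAP bear on this.

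- **Procedure, step 35.** The site will "follow up with the participant in 24-48 hours to screen for any adverse events or complications". The step is not limited to those who complete the session.
- **Withdrawal, Early Termination, or Suspension of the Investigation.** A list introduced by "The collection of data for study participants will cease in the following cases" includes "Adverse event other than death requiring withdrawal of the participant from the study". Just after the list comes the rule "No follow-up procedures for withdrawn or discontinued participants are required, unless such is required at the Investigator's discretion". Later in the same section, following participants until pending adverse events resolve is called for, but only when the study itself is terminated early.
- **Management of Adverse Event Reporting.** Under "The following information will be obtained", the list has "Date of onset and resolution". Withdrawal from the study is one of the actions that can be recorded for an event.
- **Duration of Clinical Investigation.** This section says that the investigation needs no further follow-up, which sits awkwardly with step 35.

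The Safety section refers to the Procedure for how a participant may be withdrawn, but the numbered steps contain no withdrawal rule. Nothing visible ranks these provisions.

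**The concern.** A participant withdrawn because of an adverse event has already shown a reaction to the procedure and has the strongest claim to a later check. Under one natural reading of the text, that person has the weakest mandated follow-up in the study.

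The event that caused the withdrawal would still be recorded. What could be missed is a new event after departure, or a worsening of the first one. The risk section names hematoma, clotting and infection among the possible effects of the IV, and these can appear or worsen after a visit of about 3 hours. The time limits for reporting serious and unanticipated events run from when the Investigator first learns of them, so a late event has to reach the Investigator before any clock starts.

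The SAP summarizes reported adverse events in a table. If withdrawn participants are not screened at 24-48 hours and completers are, the table mixes two levels of ascertainment. No test, passing criterion or sample-size argument depends on this.

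**Working it through.** The plan gives no figure to reproduce. The check is a comparison of the provisions, followed by an illustration of size.

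**1. Scheduled contact mandated after the participant leaves**

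| Situation | Provision applied | Mandated scheduled contact |
|---|---|---|
| Uneventful completer | Step 35 | One, at 24-48 h |
| Withdrawn for an adverse event, step 35 governs | Step 35 | One, at 24-48 h |
| Withdrawn for an adverse event, withdrawal sentence read as an exception | Withdrawal section | None; Investigator's discretion |
| Study terminated early, event pending | Withdrawal section, early-termination text | Follow-up until the event resolves |

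The problem lies in the third row. The fourth shows that the protocol already accepts follow-up to resolution as a standard, but does not extend it to an individual withdrawn because of an event.

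**2. Does the resolution date close the gap?** In part. If an event is open when a withdrawn participant leaves, its resolution date can be obtained only through later information, so some tracking is implied. No contact or schedule is set, however, and an event that begins after departure is not covered.

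**3. Do the other safeguards close it?** They reduce the risk. A clinician is present throughout, staff assess any event, steps 30-31 check fitness to leave and ask about ill effects, step 32 provides phone numbers, and the Investigator may order follow-up. None of these makes a contact after departure mandatory.

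**4. Size, with assumed rates.** The sample size of 20 is from the protocol. The documents give no rate of withdrawal, of discretionary follow-up or of later events, so the other three inputs are assumptions:

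- w = share withdrawn for an adverse event (1% to 10%; central value 5%)
- n = share of those not followed up at the Investigator's discretion (0% to 100%)
- e = share with a later event (5% to 20%; central value 10%)

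Expected participants with a later event not screened by a scheduled contact = 20 × w × n × e.

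- w = 0.05, n = 0, e = 0.10: 20 × 0.05 × 0 × 0.10 = 0
- w = 0.05, n = 0.20, e = 0.10: 20 × 0.05 × 0.20 × 0.10 = 0.02
- w = 0.05, n = 1, e = 0.10: 20 × 0.05 × 1 × 0.10 = 0.10
- Upper end, w = 0.10, n = 1, e = 0.20: 20 × 0.10 × 1 × 0.20 = 0.40

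The range is 0 to 0.40 participants. Self-report through the phone numbers given at discharge would lower every non-zero value.

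**The case against.** The strongest reply is that the texts do not contradict each other. The withdrawal section says that follow-up is not required; it does not forbid it. A site that calls everyone at 24-48 hours complies with both provisions. That is correct, and a reader who infers a flat contradiction goes further than the documents allow. What stands is that a site which calls completers only can also claim compliance, by treating the withdrawal sentence as the specific rule.

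A second reply is that steps 30-32 and step 35 belong to one numbered list. If the discharge checks apply to someone withdrawn, the later call should too. This is a reasonable reading, but the withdrawal sentence is the only text that addresses withdrawn participants by name, and it points the other way.

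Two stronger inferences are also tempting.

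- **That safety reporting stops at withdrawal.** The list of cases in which data collection ceases also includes "Participant death", yet the section on serious events says "If the event results in death of a participant, the event shall be reported", with a limit of 24 hours. The list therefore cannot end safety reporting. It may mean only study and device data capture, and this point does not rest on it.
- **That withdrawn participants have no required follow-up of any kind.** The resolution date already implies some tracking of an open event. Only the absence of a mandated scheduled contact can be supported.

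Finally, adverse-event reporting is also governed by site procedures, IRB requirements and sponsor SOPs, and some nearby text is redacted. These may settle the matter but cannot be checked here.

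**Conclusion.** The point holds as an unresolved inconsistency with a modest safety consequence. The withdrawal section makes follow-up discretionary, step 35 does not, and the visible text does not rank them. If the withdrawal sentence is treated as an exception, a participant withdrawn for an adverse event has no mandated scheduled contact after leaving and an uneventful completer has one. The exposure is mainly to new or worsening events after departure.

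The expected effect is small: 0.02 to 0.10 participants at the central rates when 20% to 100% of those withdrawn are not followed up, and 0.40 at the assumed extreme. All rates are assumptions, and the consequence depends on which provision the site applies. The study's analyses are unaffected apart from the descriptive adverse-event table. A change is worth making because it is cheap and concerns participants who have already had an event.

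**What to change.** Amend the sentence in the withdrawal section to say three things:

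- Study and device data capture stops at withdrawal.
- Any withdrawn or discontinued participant in whom the IV, blood draw or infusion was started still receives the step 35 contact at 24-48 hours, unless they refuse it.
- An adverse event open at withdrawal is followed to resolution, as the same section already provides on early termination of the study.

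Align the follow-up statement under Duration of Clinical Investigation so that it acknowledges the 24-48 h contact. Completers need no new duty, since no gap was found for them.

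The cost is a wording amendment that needs sponsor and then IRB approval, in a study with about 8 working days of data collection. The added calls are of a kind the site already makes. At the upper assumed rate of withdrawal for an event they number 20 × 0.10 = 2, plus any for participants withdrawn for other reasons. An open event may occasionally need longer follow-up.
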